## 5.4 Patients unable to provide informed consent (Scotland)

Some patients who are eligible for the trial will have a temporary impairment to their ability to provide consent. This impairment will result from the condition for which they require surgical intervention. Patients who have a long-term cognitive impairment that prevents fully informed consent will be excluded from the trial.

If the patient does not have capacity for fully informed consent due to temporary impairment, where possible the trial will be briefly discussed with them, and they will be given the Summary PIS. In accordance with guidelines from the HRA, the trial will also be discussed with the patient's Legal Representative. For the purposes of TONIC, a patient's Legal Representative will be their nearest relative (See Appendix 1 for a hierarchical list of nearest relatives). Patients with long-term incapacity are not included in this trial so patients that have appointed a Welfare Attorney or Guardian will not be eligible.

The Legal Representative must be:

- Told that they are being asked to give consent on behalf of the incapacitated adult
- Told that they are free to decide whether they wish to make this decision or not
- Told that they are being asked to consider what the adult would want, and to set aside their own personal views when making this decision
- Given sufficient information, in an understandable form, about the trial to ensure that they can make an informed decision

A Legal Representative (Nearest Relative) Information Sheet will be provided to facilitate the consent process. If the legal representative consents for the patient to be included in the trial, the legal representative will initial, sign and date the latest version of the Legal Representative (Nearest Relative) Consent Form.

If no Legal Representative is available, the patient will not be included in the trial.

It is imperative that when a Legal Representative has been consulted, that as soon as the participant is able to provide informed consent, the trial is explained to them and their written informed consent is sought. The participant will be given the PIS for delayed consent and their consent will be documented through the initialling, signing and dating of the latest version of the ICF for delayed consent.

If, at any stage, the participant refuses consent for involvement in the trial or asks to be withdrawn from the trial, their wishes must be adhered to. If the participant does not wish to

continue, they will be withdrawn from the trial. Any data collected up to the point of withdrawal will be retained and used in the trial.

For a small number of patients (<2%), it is anticipated that they will not regain consciousness/capacity within 30 days, as these patients will have already received the intervention and reached the primary outcome, their data will be retained for use in the final analysis. If these patients regain capacity after 30 days, where practical, the local research team will consent them for their involvement in the study. In the event that the patient never regains capacity or dies, then they will remain in the trial and their data will be included in the analysis.

## **5.5 Ongoing consent**

At each visit, the participant's willingness to continue in the trial will be ascertained (through the participant, personal consultee or legal representative as appropriate) and documented in the medical notes. Throughout the trial, the participant, personal consultee or legal representative will have the opportunity to ask questions about the trial. Any new information that may be relevant to the participant's continued participation will be provided. Where new information becomes available which may affect the participants' decision to continue, participant, personal consultee or legal representative will be given time to consider this information and if happy to continue they will be re-consented. Re-consent will be documented in the medical notes. The participant's right to withdraw from the trial will remain.

In the UK, if a participant loses capacity during the 90 day study period, the advice/consent of a Personal Consultee (England/Wales)/Legal Representative (Scotland) on whether the participant should remain in the study will be sought and a declaration/consent obtained as described in sections 5.3 and 5.4.

Electronic copies of the PIS and ICF will be available from the Trial Office and will be printed or photocopied onto the headed paper of the local institution.

With the participant's consent (or assent from personal consultee/legal representative), their General Practitioner (GP) will also be informed that they are taking part in the trial.

## **5.6 Additional consent**

We will also add additional statements to the ICF for the participant/personal consultee/legal representative to acknowledge that they understand that the Trial Office might in the future, for other related research, collect participant data available in NHS routine clinical datasets, including primary care data (e.g., Clinical Practice Research Datalink, The Health Improvement Network, QResearch) and secondary care data (Hospital Episode Statistics) through NHS Digital and other

central UK NHS bodies. The participant/personal consultee/legal representative will acknowledge that they understand that the Trial Office might send their name, address, date of birth, sex, NHS number (CHI number, Scotland) and trial number to the relevant national registry, and then for the national registry to link this to their data and send the information back to the Trial Office. The acknowledgement by the participant (or personal consultee/legal representative) will also allow access to other new central UK NHS databases that will appear in the future. This will allow us (subject to receipt of additional funding via another grant application) to assess longer-term impact and health service usage data without needing further contact with the trial participants.

## 6. ENROLMENT, RANDOMISATION and BLINDING

### 6.1 Identification

Patients booked for an emergency laparotomy or laparoscopy who may be eligible for inclusion in the study will be identified by the on-call surgical team with responsibility for their clinical care. Identification is through clinical handover, clinical notes, or from theatre booking lists. The clinical team will inform the patient about the study and seek permission for a member of the research team to discuss the study with them. If the patient agrees and is happy to be approached this will all be documented in the patients' medical records and the patient will be approached by a GCP trained member of the research team. This member of the research team may be either a member of the clinical team or a research nurse. The consent process will be undertaken as detailed in Section 5.

### 6.2 Screening and enrolment

Details of all patients approached about the trial will be recorded on the TONIC Participant Screening/Enrolment Log which will be kept in the ISF, and should be available to be sent to the Trials Office upon request.

Eligibility must be confirmed by a suitably qualified medical practitioner who is delegated this task on the TONIC Site Signature and Delegation Log.

### 6.3 Randomisation process

Randomisation should be performed pre-operatively for all participants.

Randomisation will be provided by BCTU using a secure online Electronic Data Capture (EDC) system (available at <https://bctu-redcap.bham.ac.uk/>), thereby ensuring allocation concealment. Unique log-in usernames will be provided to those who wish to use the online EDC system and who have been delegated the role of randomising participants into the trial as detailed on the TONIC Site Signature and Delegation Log. These unique log-in details must not be shared with other staff and in no circumstances should staff at sites access the system using another person's login details. The online EDC system will be available 24 hours a day, 7 days a week, apart from short periods of scheduled maintenance.

In the rare instance of the online system being unavailable, the trial office should be contacted and are available Monday to Friday, 09:00 to 17:00 UK time, except for bank holidays, government guided closures and University of Birmingham (UoB) closed days.

**Please note: to randomise a patient when the online system is unavailable, the TONIC Trial Office should be contacted directly via email or telephone using the contact details outlined at the front of the protocol.**

## **6.4 Randomisation procedure**

After eligibility has been confirmed and informed consent (or declaration for those who cannot provide informed consent) has been received, the participant can be randomised into the trial using the online EDC system. A worksheet replicating the electronic randomisation form and the eligibility and consent form may be used to collate the necessary information prior to randomisation. All questions and data items on the online Randomisation Form and the eligibility and consent form must be answered prior to a potential participant being randomised into the trial and a Trial Number being issued.

Following randomisation, a confirmatory e-mail will be sent to the local PI, person randomising and nominated site contacts. The confirmatory email will also be sent to the TONIC Trial mailbox.

The local research team should add the participant to the TONIC Participant Recruitment and Identification Log which links participants with their Trial Number. The PI must maintain this document securely and it must not be submitted to the Trial Office. The TONIC Participant Recruitment and Identification Log should be held in strict confidence.

## **6.5 Randomisation method**

Participants will be randomised at the level of the individual in a 1:1 ratio to either early administration of PN or standard care via a central secure web-based randomisation system available 24 hours/day at the BCTU. A minimisation algorithm will be used within the randomisation system to ensure balance in the intervention allocations over the following variables:

- NELA risk (<5 OR ≥5%) [33]
- Nutrition Risk Score (<3 OR ≥3) [34]
- Recruiting site (hospital name).

To avoid the possibility of the intervention allocation becoming predictable, a random element will be included in the algorithm. Full details of the randomisation specification will be stored in a confidential document at BCTU.

## **6.6 Blinding**

This is an unblinded trial. It is not possible to blind participants or clinicians due to the interventions being used. It is not possible to blind outcome assessors as some outcomes are related to the delivery of the intervention.

All statisticians will be blind until the first version of the Statistical Analysis Plan (SAP) is approved, and one statistician ([name]) will remain blind until final analysis.

## **6.7 Informing the participant's GP and other parties**

If the participant has agreed, the participant's GP should be notified that they are in the TONIC trial, using the TONIC GP Letter.

The trial specific GP Letter will be sent to the participant's GP directly from the site that randomised the patient into the trial.

## 7. TRIAL INTERVENTION

The trial intervention is the early administration of PN, compared to standard nutritional care.

### 7.1 Trial intervention(s)

Participants will be randomised to receive:

- Early PN through central venous catheter (CVC) or PICC, commencing within 48 hours of emergency laparotomy/laparoscopy, with biochemistry monitoring as per NICE Clinical Guideline 32[33]
- Standard nutritional care, which may include no support, oral nutritional supplements or nasoenteric feeding at anytime point. Clinicians can use PN in the control group, but, as per NICE guidance, not before 5 days post-surgery unless there is pressing clinical need.

### 7.2 Trial intervention: Parenteral Nutrition

The trial intervention is intentionally pragmatic. Patients randomised to the intervention arm will receive early PN which will be administered intravenously and should be delivered either through a dedicated lumen of a central line placed at operation, or through a PICC line. These lines are inserted by anaesthetists or by specialised vascular access services, depending on local service specifications. Line access may be secured at any point from randomisation to commencement of intervention. Placement of these lines will be confirmed with a plain radiograph of the chest and is undertaken as per local processes, using aseptic techniques. Blood tests are performed prior to commencement of PN to ensure sodium, potassium, magnesium, and phosphate are in the correct range

PN is available pre-formulated from multiple suppliers in the UK. The trial does not specify or mandate the use of any particular brand; participating sites should continue to use the PN formulation routinely employed in their standard clinical practice. Sites will already have familiarity with a particular brand and will use this for the trial. PN provides carbohydrates, lipids, amino acids, vitamins, trace elements, electrolytes and water. These amounts vary according to the supplied bag. An appropriate base PN bag is selected based upon the nutrients required, particularly calories. Additional electrolytes can be added, tailored to the patient's biochemistry. The administration of PN is defined in UK guidance from NICE[26], which provides guidance on calculating calorie requirements. Sites will calculate appropriate rates of PN to be administered prior to commencement. Out of hours, this may include administering a volume defined by local out-of-hours feeding protocols, rather than a dose tailored to exact calorie requirements. At the commencement of PN, dosing is at a reduced rate to avoid metabolic consequences. This is slowly increased with ongoing monitoring of blood tests for evidence of electrolyte disturbance (e.g. abnormal sodium, potassium, phosphate, or magnesium levels). Blood tests (biochemistry including renal and liver function) are required daily for the first week of administration and

---

remain daily until blood tests results are stable. Following this, they can be decreased in frequency as per local protocols. This is in line with NICE guidance. PN is prescribed on a 24-hour basis and would continue until the participant has recovered gastrointestinal function, sufficient to allow adequate enteral intake. This is determined by the nutrition team in collaboration with the surgical team.

Some people are at higher risk of complications such as refeeding syndrome. This is a condition characterised by low serum concentrations of potassium, magnesium and phosphate. The electrolyte imbalance may cause neurologic, pulmonary, cardiac, neuromuscular, and hematologic symptoms—many of which, if severe enough, may result in death. Testing of additional nutrients such as B12 and Zinc may also be performed to ensure they are within normal range. Thiamine and B12 may also be administered prior to starting PN according to local protocols. Depending on clinical team decisions, the patient may have oral intake as well as receiving PN.

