## 3. TRIAL DESIGN AND SETTING

### 3.1 Trial design

The TONIC trial is a multi-centre, two-arm, parallel group, superiority, individual participant-RCT with 1:1 allocation to early PN or standard nutritional care with an internal pilot and a full economic evaluation. Patients undergoing NELA eligible emergency laparotomy or laparoscopy will be randomised to either early PN started within 48 hours of emergency laparotomy/laparoscopy or standard nutritional care.

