**Table 2: Key Steps in the intervention and control arms**

|                  | Standard Care   | Intervention (Early Parenteral Nutrition <48 hours post-operatively)  |
|------------------|---|---|
| Why       | Reflects current practice in the NHS; a broadly reactive approach to perioperative nutrition. | Early nutrition may reduce complications and improve clinical outcomes by preventing nutritional deterioration and its sequelae. The gastrointestinal tract is typically non-functional following surgery, so parenteral route is preferred initially |
| Materials | Management in line with local policies for emergency  | Venous access with PICC/CVC   |

|                          |   |  |
|--------------------------|---|--|
|                          | laparotomy recovery and local nutrition policies.   | TPN is required, along with local nutrition policies.  |
| Procedures        | All patients screened with Malnutrition Universal Screening Tool (MUST) or equivalent at admission, and then weekly. Scores of three or more should lead to dietitian review. | Line placed to facilitate feeding, and chest x-ray performed to confirm placement. Baseline blood tests reviewed prior to commencement and key electrolytes replaced prior to commencement of PN or added to PN bag. May also receive B12/Thiamine if high-risk of refeeding syndrome. Energy requirements (Basal metabolic rate plus additional energy needs) are estimated in line with local policies and NICE guidance[25]. Feed is initially commenced at a low rate/volume, building to full energy requirements over a few days, with daily monitoring of electrolytes for the first 7 days. Additional safety tests including liver function monitoring are also performed, as well as monitoring for line sepsis. |
| Who provides      | Oral nutritional supplements can be prescribed at the direction of a nutrition team member, or a member of the surgical team.   | Access is provided by a vascular access specialist (either nurse, anaesthetist, or vascular radiologist depending on local service set up). Assessment of nutritional needs and requirements is led by the nutrition team and prescribed in conjunction with the responsible surgical team.  |
| How               | Provided at an individual level and on a face to face basis.  | Provided at an individual level and on a face to face basis.   |
| Where             | On ward or critical care  | On ward or critical care   |

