#### Comprehensive Complication Index

The CCI is based on the conventional CDC which has been widely used in surgical research[36, 37]. The CCI is the mathematical summation of complications graded using the conventional CDC and takes into account the number and severity of each complication to obtain a value from 0 (no complications) to 100 (death). As all post-operative complications are included it is more sensitive than other surgical morbidity endpoints[38]. There is an online tool available to calculate the CCI at [CCICalculator.com](http://CCICalculator.com).

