### **At discharge:**

The complications experienced by the participant post-op up to discharge will be captured from clinical notes, and from consultation with the clinical team. The research team, in conjunction with the local PI will assign a Clavien Dindo classification to complications.

Process measures (time to line insertion) will be captured from clinical notes.

Nutrition outcomes will be captured from clinical records. Intended dosing of PN (total calorie requirement), and proportion of this administered, will be captured from clinical records.

The participant will undertake a 30 second sit to stand test. This should be performed on the day of discharge. However, when this is anticipated to occur over a weekend with no research staff available, this may occur up to two days prior to discharge. EQ-5D-5L, PRO-diGI, patient satisfaction visual analogue scale, and QoR-15 will be captured at this timepoint, with completion either directly by the patient or administered by a member of the research team. Barthel Index will be completed by a member of the research team. Discharge details will also include details of discharge destination (usual residence, residential, or nursing home).

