## 14. STATISTICAL CONSIDERATIONS

### 14.1 Sample size

The CCI uses a combination of frequency and weighting to score complications along the CDC framework[36]. Previous literature has demonstrated the standard deviation of this measure to be ~27 for this population[18]. Perinel et al demonstrated an 8-point difference in CCI following early TPN in the elective setting, which corresponded to a 12% reduction in grade III-V complications[43]. Based on the increased acuity and complexity of this patient group, we believe a 6 point reduction in CCI to be a feasible and relevant effect size. A 6-point difference is equivalent to downgrading a class III complication to a class II complication[29]. Allowing for up to 5% attrition, 90% power, 5% two-sided significance threshold, a sample size of 449 participants in each arm is needed (total 898).

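### Tests required in the PN arm have no set counterpart in controls, so low-grade complications in the primary CCI may be recorded more often with early PN

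*Protocol*

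**What the plan says.** **PN arm.** Section 7.1 makes biochemistry monitoring part of the allocated treatment. Section 7.2 asks for electrolytes to be checked before PN starts and then sets the frequency: "Blood tests (biochemistry including renal and liver function) are required daily for the first week of administration and" they continue daily until stable, after which local protocols govern. Table 2 (Section 7.4) adds "Line placed to facilitate feeding, and chest x-ray performed to confirm placement", together with liver function tests and monitoring for line sepsis.

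**Control arm.** The control column of Table 2 asks for malnutrition screening at admission and weekly, and otherwise refers to local recovery and nutrition policies. Section 7.3 describes control care as variable and reactive. Neither place sets a blood test or imaging schedule.

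**Primary outcome.** On the CCI, Section 8.2.1 says: "As all post-operative complications are included it is more sensitive than other surgical morbidity endpoints". Section 9 (At discharge) gives the source: "The complications experienced by the participant post-op up to discharge will be captured from clinical notes", supplemented by the clinical team, with the research team and local PI assigning the grade. Section 6.6 says outcome assessors cannot be blinded. Section 1.2.4 points out that several minor complications can outscore one serious one.

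The protocol has no rule for complications known only from a test result. Section 14.2.1 leaves the detail of CCI scoring to the SAP.

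**The concern.** The primary outcome depends on what reaches the clinical notes, and that depends partly on how often someone looks. One arm has required daily biochemistry for at least a week and a required radiograph. In the other, testing is whatever the site would have done anyway. A mild rise in creatinine, a low potassium or an incidental chest finding can occur equally often in both arms and still be written down more often in one.

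This is separate from the arm-specific event list in Section 10.5.2, where metabolic and line events are listed for collection only in participants allocated to PN (Table 8). Acute kidney injury and pneumonia are listed for all participants (Table 7), yet daily renal function and the placement radiograph are required only with PN. Identical forms in both arms would leave this difference in detection.

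At stake is the meaning of the between-arm difference. The objective is whether early PN reduces complications. Any part of the difference that comes from unequal testing is measurement error, and it would most likely hide benefit.

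**Working it through.** **1. Reproduce the planned sample size.** Inputs from Sections 14.1 and 3.1: "a 6 point reduction in CCI to be a feasible and relevant effect size"; "standard deviation of this measure to be ~27 for this population"; "Allowing for up to 5% attrition, 90% power, 5% two-sided significance threshold"; "1:1 allocation to early PN or standard nutritional care".

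- n per arm = 2 × SD² × (1.96 + 1.2816)² / difference² = 2 × 729 × 10.507 / 36 = 425.5, rounded up to 426.
- With 5% attrition: 426 / 0.95 = 448.4, rounded up to 449 per arm, 898 in total.

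This matches the protocol, so the sample-size arithmetic is not in question.

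**2. Compare what is required in each arm.**

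| | PN arm | Control arm |
|---|---|---|
| Blood tests | Before PN, daily for at least the first week of PN, then by local protocol | No schedule set; local policy |
| Chest imaging | One radiograph at line placement | None set; local policy |
| Line sepsis | Monitored | None set |
| Events entering the CCI | All grades, from notes | All grades, from notes |
| Grading | Unblinded | Unblinded |

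The first three rows differ and the last two do not. An all-grade score with the same source is therefore fed by different required testing.

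**3. Why low-grade events can move the score.** Section 14.2.1 quotes a median CCI of 21 with an interquartile range of 0 to 29. A lower quartile of 0 means that at least a quarter of participants are expected to score 0, and a single recorded minor event takes such a participant off zero.

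**4. Illustrate the consequence.** Let b be the points that extra detection adds to the PN-arm mean. The protocol gives no value for b, so the values below are assumptions. Roughly, b is the share of PN participants with an extra detected event times the net points each adds: for example 0.10 × 5 = 0.5, 0.20 × 5 = 1 and 0.20 × 10 = 2.

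- Standard error of the difference = 27 × √(2/426) = 1.85.
- Power for a true 6-point benefit = Φ((6 − b)/1.85 − 1.96).

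| b (assumed) | Expected observed difference | Power |
|---|---|---|
| 0 | 6.0 | 90.0% |
| 0.5 | 5.5 | 84.4% |
| 1 | 5.0 | 77.1% |
| 2 | 4.0 | 58.0% |

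The calculation assumes no offset from earlier detection averting a worse grade.

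**The case against.** The strongest reply is that monitoring belongs to the treatment under test. Section 7.1 defines the arm that way, the trial is pragmatic, and complications that PN really causes should count. This stands, and it is why the all-complication CCI should remain primary. It does not cover an event equally common in both arms but recorded more often in one.

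Second, controls are seriously ill surgical patients who may well have frequent bloods and imaging under local policy, and some will receive PN later with its monitoring. This also stands: the asymmetry is in what the protocol requires, and the real gap in testing is unknown and could be small. A reader might infer from Table 4, which ticks routine bloods at baseline only, that controls go untested afterwards. The table does not support that. It is not split by arm and omits the PN arm's daily bloods as well.

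Third, correcting an electrolyte in the PN bag is described as part of delivering and tailoring PN. The protocol nowhere calls such an adjustment a complication, so it cannot be assumed that every abnormal result would be scored.

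Fourth, CCI scoring and sensitivity analyses are deferred to the SAP (Sections 14.2.1 and 14.2.4), so it would be wrong to claim that no planned analysis addresses this. However, an analysis can separate test-only events only if the CRF identifies them, and it cannot recover control events that were never tested for. Data collection is governed by the protocol.

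**Conclusion.** The point holds as an asymmetry in required testing that feeds an all-grade, notes-based primary outcome graded without blinding. Test-detected low-grade events may be recorded more often in the PN arm. The likely direction is against early PN, but this is not certain, because earlier detection might prevent some higher grades.

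The size cannot be estimated from the protocol. The falls in power from 90% to 84%, 77% or 58% follow from assumed inflations of 0.5, 1 and 2 points, with SD 27, 426 evaluable participants per arm and a true 6-point benefit. They show how sensitive the trial would be, not what will happen.

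Two stronger readings should be resisted. A reader might infer that all the extra testing runs for exactly as long as PN does. The radiograph is a single check at line placement, and the bloods taper by local protocol; that they end with PN is a reasonable inference but is not written. A reader might also conclude that the trial will be biased by a material amount. That would need the frequency of testing in controls, which is not given.

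**What to change.** In Sections 8.2.1 and 9, add one item to the complication record, worded identically for both arms: whether the complication was identified only from a laboratory or imaging result, without symptoms or clinical consequence, however it was detected or treated. Keep the all-complication CCI as the primary outcome. Pre-specify a sensitivity analysis in which the CCI is recalculated without the flagged events in both arms, and report it beside the primary result, so that genuine PN harms stay visible and the reader can see whether the conclusion depends on unequal testing.

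Any threshold for counting an event must apply in the same way to both arms. A rule that discounted findings from PN monitoring, or abnormalities corrected through the PN bag, would act almost only on PN recipients. The same abnormality corrected by another route in a control would still count, and the bias could turn in favour of PN.

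The cost is one extra CRF item and one extra analysis. The flag will itself be set by unblinded staff, so its wording should leave little to judgement. No change to clinical monitoring is proposed.
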